12.5.1 Once per week (Weeks 1 through 16)

The following procedures will be performed at one visit per week from Weeks 1 through 16:

- Physical examination
- Assessment of Adverse Events and Concomitant Medications (including review of subject diary for bleeding and FVIII use)
- Vital Signs
- Liver Function Tests (refer to Table 9.7.8.3.1) central laboratory assessment
 - LFTs may be monitored more or less frequently (and in particular when ALT values are >1.5x ULN) based on discussion between the Medical Monitor and the Investigator and review of subject data.
- Samples for FVIII Assays central laboratory assessment
 - FVIII activity level (one-stage APTT)
 - FVIII activity level (chromogenic FXa assay)
 - FVIII coagulation activity exploratory assay
 - o Bethesda assay (with Nijmegen modification) for hFVIII inhibitor level
 - FVIII antigen (ELISA)

Note: If a subject has used FVIII within 72 hours of a measurement day, all efforts should be made to obtain FVIII activity measurements when a 72-hour interval without FVIII use is achieved. The 72-hour wash-out period is only intended for subjects who have achieved FVIII \geq 5 IU/dL at 16 weeks after BMN 270 infusion and who have not resumed standard of care FVIII replacement therapy.

• Central assessment of FVIII activity level should be performed 1x/week from Week 1 through Week 16

BOMARIN	270-201 – Amendment 6	Page 77
---------	-----------------------	---------

- Liver Function Tests (refer to Table 9.7.8.3.1) local laboratory assessment
 - LFTs may be monitored more or less frequently (and in particular when ALT values are >1.5x ULN) based on discussion between the Medical Monitor and the Investigator and review of subject data.
- FVIII activity level local laboratory assessment
 - FVIII activity level (one-stage APTT)
 - FVIII activity level (chromogenic FXa assay)
- PBMC collection

12.5.2 Week 1 – Day 2 and Day 4

On Day 2 and Day 4 of Week 1, the following procedures will be performed:

- PCR of vector DNA in blood, saliva, urine, semen, and stools (Day 2 and Day 4)
- Samples for FVIII Assays (Day 4 only) central laboratory assessment
 - FVIII activity level (one-stage APTT)
 - FVIII activity level (chromogenic FXa assay)
 - FVIII coagulation activity exploratory assay
 - Bethesda assay (with Nijmegen modification) for hFVIII inhibitor level
 - FVIII antigen (ELISA)

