14.3 Primary and Secondary Efficacy Analysis

The subjects will be followed in a longitudinal manner and all the relevant information will be collected. The analysis of the data will be descriptive in nature. Descriptive statistics include the number of subjects, mean, median, standard deviation, minimum, and maximum for continuous variables and count and percent for categorical variables. Efficacy variables will be summarized by dose cohort at each time point. Relationship between dose and efficacy results will be examined.

Data collected in a longitudinal manner may be analyzed using longitudinal methods such as mixed effect model which takes into account the correlation among the observation taken at various time points within a participant. Efficacy is a secondary endpoint, defined as biologically active hFVIII at \geq 5 IU/dL by chromogenic FXa and/or one-stage APTT assay as measured by the central laboratory at 16 weeks following study treatment. hFVIII activity will be assessed weekly during the study period. We can only assess the true steady state of hFVIII protein produced from BMN 270 after a minimum of 72 hours has elapsed since the last infusion of FVIII protein concentrates.

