7 INTRODUCTION

Haemophilia A (HA) is an X-linked recessive bleeding disorder that affects approximately 1 in 5,000 males (Nathwani, 1992, Baillieres Clin.Haematol.). It is caused by mutations in the factor VIII (FVIII) gene that codes for FVIII protein, an essential cofactor in the coagulation cascade. Clinical manifestations of severe FVIII deficiency are frequent unprovoked bleeding episodes in joints and soft tissues causing permanent disability and occasionally death mostly after brain haemorrhage. Treatment in Western (Berntorp, 2012, Haemophilia.) countries consists of intravenous injection of plasma derived or recombinant FVIII protein concentrates at the time of a bleed, or prophylactically, to prevent bleeding episodes. The short half-life for FVIII (~8-12 hours) necessitates frequent infusions and makes this treatment prohibitively expensive for the majority of the world's haemophilia A patients. These individuals develop debilitating arthropathy and have a substantially increased risk of death from haemorrhage in life (Stonebraker, 2010, Haemophilia.). Chemical modification or bioengineering of FVIII may improve half-life to 18-19 hours (Kaufman, 2013, Blood). However, these long acting FVIII variants do not eliminate the need for lifelong FVIII protein administration (Hay, 2012, Blood).

Gene therapy offers the potential of disease-modifying therapy by continuous endogenous production of human FVIII following a single administration of vector. Haemophilia A is well suited for this approach because its clinical manifestations are attributable to the lack of a single gene product (FVIII) that circulates in low amounts (100-200 ng/ml) in the plasma. Tightly regulated control of gene expression is not essential and a modest increase in the level of FVIII (a plasma level of 2 ng/ml protein leads to a 1% expression) can ameliorate the severe phenotype (Srivastava, 2013, Haemophilia.); thus the therapeutic goal for gene therapy is a modest increase in hFVIII. Finally, the consequences of gene transfer can be assessed using simple quantitative rather than qualitative endpoints that can be easily assayed in most clinical laboratories.

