Treatment of severe HA presently consists of intravenous injection of plasma derived or recombinant human FVIII protein (rhFVIII) concentrates both as prophylaxis 2-4 times per week, and at the time of a bleed, to prevent or control bleeding episodes, respectively. The half-life for FVIII (12-18 hours for most approved products) necessitates frequent infusions, and although a major advance in the treatment of HA, it remains common for severe HA patients to continue to have multiple bleeding events on treatment (mean of 1 to 7 episodes/year with prophylaxis and up to 30 to 50 episodes/year for on demand treatment) (Nagel, 2011, Haemophilia.). The consequence of multiple bleeding events is the development of an underlying pathology that contributes to debilitating multiple-joint arthropathy and substantially increased risk of death (Nagel, 2011, Haemophilia). Chemical modification (e.g. direct conjugation of polyethylene glycol (PEG) polymers) and bioengineering of FVIII (e.g. FVIII-Fc fusion proteins) improve half-life by approximately 50%, and thus, show promise in reduced dosing and maintaining activity levels above 1%trough (Stonebraker, 2010, Haemophilia.), (Mahlangu, 2014, Blood). However, these longer acting FVIIIs remain dependent on multiple infusions to maintain critical levels of FVIII activity in severe HA patients. There is therefore a strong unmet need for a fully preventive treatment of HA to give patients a FVIII level compatible with a normal and haemorrhage-free life.

Proprietary and Confidential

BOMARIN	270-201 – Amendment 5	Page 28
---------	-----------------------	---------

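### One 72-hour interval for all FVIII products is long enough at the protocol's 8-12 h half-lives but not at its 18-19 h half-lives, where residual concentrate can carry a low expresser over the 5 IU/dL cut

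*Protocol*

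**What the plan says.** Protocol Section 14.3 (Amendment 6) states that the true steady state of FVIII produced from BMN 270 can be assessed only "after a minimum of 72 hours has elapsed since the last infusion of FVIII protein concentrates". The sampling note in Section 12.5.1, repeated at later visits, asks that after recent FVIII use "all efforts should be made to obtain FVIII activity measurements when a 72-hour interval without FVIII use is achieved". Section 9.7.2 carries the same instruction. None of these depends on which product was infused.

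Response is a binary cut, FVIII activity of at least "5 IU/dL by chromogenic FXa and/or one-stage APTT assay as measured by the central laboratory at 16 weeks following study treatment", so a high reading in either assay is enough. The same 5 IU/dL level is used at Week 3 for escalation in Cohorts 1-3 and at Week 8 for expansion of Cohort 4 (Section 9.1).

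The protocol gives several half-lives:
- Section 7: "The short half-life for FVIII (~8-12 hours) necessitates frequent infusions".
- Section 7, for modified products: "Chemical modification or bioengineering of FVIII may improve half-life to 18-19 hours".
- Section 7.3: "half-life for FVIII (12-18 hours for most approved products) necessitates frequent infusions".
- Section 7.3, for PEG-conjugated and Fc-fusion products, which are said to "improve half-life by approximately 50" per cent.

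Section 9.4.8.1 lets subjects take FVIII whenever needed, names no product restriction, and has them record use in a diary. The half-life text is on the Amendment 5 pages. The corresponding Amendment 6 pages are not shown, but its table of text revisions lists no change to Section 7.

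**The concern.** The 72 hours is there so that the measured activity can be credited to the vector. Whether it succeeds depends on the half-life of the last product infused, and the protocol's own half-lives differ more than twofold. None of the assays is described as separating infused FVIII from transgene FVIII, and Section 7.1 says the transgene product closely matches an infused one.

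Any residual is added to the subject's own level. Someone expressing far above 5 IU/dL is classified the same either way. Someone expressing little can be pushed over the cut, and low expressers are the subjects most likely to bleed and infuse. The error therefore runs towards more responders. With at most 15 subjects over four dose levels, one misclassified subject is a visible share of a cohort, and finding the dose that achieves 5 IU/dL at Week 16 is a primary objective (Section 8).

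**Working it through.** **The stated figure.** The protocol gives no derivation for 72 hours, so there is no calculation to reproduce. It equals 72/12 = 6 half-lives at 12 h and 72/8 = 9 at 8 h.

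**Inputs.** Interval 72 h (Sections 14.3 and 12.5.1). Cut 5 IU/dL (14.3). Half-lives 8-12 h and 18-19 h (Section 7); 12-18 h and about 50% more for modified products (7.3). Baseline activity at most 1 IU/dL (9.3.1). The post-infusion peak is not given; 50-100 IU/dL is assumed, 100 being normal on the protocol's scale, where 5% is 5 IU/dL.

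**Formulas (one-compartment, first-order decay).**
- Fraction left = 2^(-72/half-life).
- Residual = peak × fraction.
- Peak that leaves 5 IU/dL = 5 / fraction.

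| Half-life | Half-lives in 72 h | Left at 72 h | Residual, peak 50 | Residual, peak 100 | Peak leaving 5 IU/dL |
|---|---|---|---|---|---|
| 8 h | 9.0 | 0.2% | 0.1 | 0.2 | 2560 |
| 12 h | 6.0 | 1.6% | 0.8 | 1.6 | 320 |
| 18 h | 4.0 | 6.25% | 3.1 | 6.3 | 80 |
| 19 h | 3.8 | 7.2% | 3.6 | 7.2 | 69 |
| 27 h (derived: 18 h × 1.5) | 2.7 | 15.7% | 7.9 | 15.7 | 32 |

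Residuals and peaks are in IU/dL.

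**Low expressers.** At a peak of 50, a subject expressing 2 IU/dL would read 2 + 3.1 = 5.1 at 18 h and 2 + 3.6 = 5.6 at 19 h. With baseline activity of 1 IU/dL and no expression, the peak needed falls to 4/0.0625 = 64 at 18 h and 4/0.0723 = 55 at 19 h.

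**How long the exposure lasts.** From a peak of 100, concentrate alone falls to 5 IU/dL at 18 × log2(20) = 78 h, or 19 × log2(20) = 82 h. So 6-10 h past the 72-hour mark it no longer reaches the cut by itself, although it still adds to whatever is expressed.

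**Matching what 72 h gives at 12 h.** Six half-lives is 108 h at 18 h and 114 h at 19 h, leaving 1.6% in each case.

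**The case against.** The best reply is that 72 hours is worded as a minimum, so the protocol never says that every 72-hour sample is clean. That is right about the wording, but 72 hours is the only criterion sites are given, and nothing asks for a longer wait after a longer-acting product.

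The effect is also conditional, and this stands. The peak is assumed. At 50 IU/dL the residual at 18-19 h is below 5. At 100 the concentrate alone is under 5 by 78-82 h. The documents do not show that any subject uses a modified product, although 18 h is also the top of the range Section 7.3 gives for most approved products.

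Three stronger readings are tempting, and the documents do not support them:
- **Residuals of 7.9-15.7 IU/dL as the expected case.** These need a 27 h half-life, which is stated nowhere. It comes from adding 50% to the top of the 12-18 h range, whereas the stated 18-19 h fits 50% added to 12 h.
- **Distorted escalation.** By the Amendment 4 summary nine subjects had been dosed, seven of them at 6E13 vg/kg, so escalation to the highest dose had already happened. Two of those seven were above the upper limit of normal, nowhere near a 5 IU/dL borderline.
- **An unprotected mechanical cut.** The analysis is descriptive, central activity is measured weekly, individual profiles are planned, and the Data Review Board sees individual data. A transient residual may be visible against neighbouring values. This protection is partial, because the response count has no rule for using it.

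That the matter belongs in the SAP is only partly an answer. The SAP can define which samples count, but the sampling criterion is set here, and an SAP cannot recover samples that were never sought at the right time.

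Finally, Section 12.5.1 limits the wash-out to subjects at 5 IU/dL or more at Week 16 who have not resumed standard replacement. Who is covered is a separate question, but it means that lengthening the interval would not by itself reach the low expressers. The analysis rule has to apply to every sample.

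**Conclusion.** The point holds in a limited form. The single 72-hour criterion is adequate at half-lives of 8-12 h and inadequate at 18-19 h, where 6.25-7.2% of the infused activity remains. With assumed peaks of 50-100 IU/dL that is 3.1-7.2 IU/dL: enough alone to meet the cut when the peak exceeds about 69-80 IU/dL, and enough at a peak of 50 to lift a subject expressing about 2 IU/dL. If 27 h applied, the residual would be larger, but that figure is derived.

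The bias is upward and touches only low expressers who infused a longer-acting product shortly before sampling. The conclusion rests on first-order decay, the protocol's half-lives and the assumed peaks. How many subjects are affected cannot be determined from the documents.

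**What to change.** In Sections 9.7.2 and 14.3 and the FVIII sampling notes:

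1. Record the product and the time of the last infusion with each central sample.
2. For the response analysis, let the validity interval follow the product's half-life, for example the six half-lives that 72 h gives at 12 h (108 h at 18 h, 114 h at 19 h). Flag earlier samples, from any subject, as not attributable to BMN 270 alone.
3. If the Week 16 sample is flagged, use the nearest valid central sample within a pre-stated window around Week 16. Moving simply to the next weekly visit is not enough: with the ±48 h visit window, consecutive visits can be 168 − 96 = 72 h apart, and without a limit the endpoint could drift.
4. Keep a subject with no valid sample in the denominator and count him as not having shown response. Missing data are not imputed, so frequent infusers would otherwise drop out and push the response rate up.
5. Report the analysis with all 72-hour samples as a sensitivity analysis.
6. Show the flag to the Data Review Board whenever it reviews activity against 5 IU/dL.
7. Reconcile the 8-12 h half-life in Section 7 with the 12-18 h in Section 7.3.

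This is a rule about which samples count; FVIII treatment is not delayed or changed. The cost is amendment wording and two data fields. Some samples from subjects on longer-acting products will be flagged, and the response count may be slightly lower.

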14.4 Immunogenicity

Analysis of neutralizing antibody response and other immunological parameters will be primarily descriptive and involve both inter-participant and intra-participant comparisons

14.5 Pharmacodynamic Analyses

The FVIII antigen and activity level as measured by an Elisa (antigen level) and by a one-stage APTT and/or chromogenic FXa assay (activity level), will be used for plasma

BIOMARIN270-201 – Amendment 6Page 90	
--------------------------------------	--

profiles; FVIII activity will be used to determine PD parameters. Traditional PK analysis is not applicable.

If supported by FVIII activity data, non-compartmental analysis and observation will be used to estimate individual PD parameter values of C_b (baseline), C_{ss} (steady state), T_{ss} (time to steady state), C(t) and AUC(0-t) where t is 16 weeks. Other parameters that may be used to describe individual FVIII protein and activity plasma profiles are C_{max} (maximum concentration) and C_{avg} (average concentration, AUC(0-t)/t). The parameters will be summarized using descriptive statistics.

14.6 Safety Analysis

The Medical Dictionary for Regulatory Activities terminology (MedDRA) will be used by the Sponsor to assign system organ class and preferred term classification to events and diseases, based on the original terms entered on the CRF.

All AEs will be coded using MedDRA. The incidence of AEs will be summarized by system organ class, preferred term, relationship to study drug, and severity. A by-subject listing will be provided for those subjects who experience a serious AE (SAE), including death, or experience an AE associated with early withdrawal from the study or study drug. Hepatitis is of interest, and the percentage of subjects who report hepatitis will be presented.

Clinical laboratory data will be summarized by the type of laboratory test. For each clinical laboratory test, descriptive statistics will be provided on Baseline as well as all subsequent visits. Descriptive statistics for physical examination results and vital signs will also be provided.

Detailed statistical methods will be provided in the SAP.

14.7 Determination of Sample Size

No formal sample size calculations based on statistical power were performed.

The sample size is determined based upon clinical consideration and could detect a strong clinical efficacy signal. Up to 15 subjects may be dosed in the study; the actual number of subjects will depend on the criteria for dose escalation.

14.8 Analysis Populations

The Safety analysis population is defined as all enrolled subjects who receive any study drug. The analysis of safety data will be performed on Safety Set.

BOMARIN	270-201 – Amendment 6	Page 91
---------	-----------------------	---------

The Full Analysis Set (FAS) is defined as all enrolled subjects who receive study drug and have at least one Baseline and post-Baseline assessment. The FAS will be used for efficacy analysis.

14.9 Changes in the Conduct of the Study or Planned Analyses

Only BioMarin may modify the protocol. Any change in study conduct considered necessary by the Investigator will be made only after consultation with BioMarin, who will then issue a formal protocol amendment to implement the change. The only exception is when an Investigator considers that a subject's safety is compromised without immediate action. In these circumstances, immediate approval of the chairman of the IRB/IEC/REB must be sought, and the Investigator should inform BioMarin and the full IRB/IEC/REB within 2 working days after the emergency occurs.

With the exception of minor administrative or typographical changes, the IRB/IEC/REB must review and approve all protocol amendments. Protocol amendments that have an impact on subject risk or the study objectives, or require revision of the ICF, must receive approval from the IRB/IEC/REB prior to their implementation.

When a protocol amendment substantially alters the study design or the potential risks or burden to subjects, the ICF will be amended and approved by BioMarin and the IRB/IEC/REB, and all active subjects must again provide informed consent.

Note: If discrepancies exist between the text of the statistical analysis as planned in the protocol, and the final SAP, a protocol amendment will not be issued and the SAP will prevail.

BOMARIN	270-201 – Amendment 6	Page 92
---------	-----------------------	---------

15 DATA REVIEW BOARD

There will be no formal DMC for this study, however a safety and efficacy evaluation board (the Data Review Board [DRB]) composed of the investigator representatives and the Sponsor will be established.

The DRB will review safety and efficacy on an ongoing basis. The DRB will meet prior to dose escalation or dose expansion to assess available subject safety and efficacy data and make recommendations with regards to the conduct of study. Should a safety signal arise, including one which may warrant a halt of study enrollment, the DRB will promptly convene for further assessment of subject safety. Notification of all DRB meetings and meeting outcomes will be sent to participating sites.

BIOMARIN	270-201 – Amendment 6	Page 93
----------	-----------------------	---------

16 COMPENSATION, INSURANCE AND INDEMNITY

There will be no charge to study subjects to be in this study. BioMarin will pay all costs of tests, procedures, and treatments that are part of this study. In addition, after IRB/IEC/REB approval, BioMarin may reimburse the cost of travel for study-related visits. BioMarin will not pay for any hospitalizations, tests, or treatments for medical problems of any sort, whether or not related to the study subject's disease that are not part of this study. Costs associated with hospitalizations, tests, and treatments should be billed and collected in the way that such costs are usually billed and collected.

The Investigator should contact BioMarin immediately upon notification that a study subject has been injured by the IP or by procedures performed as part of the study. Any subject who experiences a study-related injury should be instructed by the Investigator to seek medical treatment at a pre-specified medical institution if possible, or at the closest medical treatment facility if necessary. The subject should be given the name of a person to contact to seek further information about, and assistance with, treatment for study-related injuries. The treating physician should bill the subject's health insurance company or other third party payer for the cost of this medical treatment. If the subject has followed the Investigator's instructions, BioMarin will pay for reasonable and necessary medical services to treat the injuries caused by the IP or study procedures, if these costs are not covered by health insurance or another third party that usually pays these costs. In some jurisdictions, BioMarin is obligated by law to pay for study-related injuries without prior recourse to third party payer billing. If this is the case, BioMarin will comply with the law.

BOMARIN	270-201 – Amendment 6	Page 94
---------	-----------------------	---------

17 CASE REPORT FORMS AND SOURCE DOCUMENTS

Electronic case report forms will be provided for each subject. The Investigator must review and electronically sign the completed CRF casebook to verify its accuracy.

CRFs must be completed using a web-based application developed and validated. Study site personnel will be trained on the application and will enter the clinical data from source documentation. Unless explicitly allowed in the CRF instructions, blank data fields are not acceptable.

In the event of an entry error, or if new information becomes available, the value will be corrected by deselecting the erroneous response and then selecting or entering the factual response. In compliance with ICH GCP Guidelines and 21 CFR Part 11, the system will require the personnel making the correction to enter a reason for changing the value. The documented audit trail will include the reason for the change, the original value, the new value, the time of the correction and the identity of the operator.

BioMarin's policy is that study data on the CRFs must be verifiable to the source data, which necessitates access to all original recordings, laboratory reports, and subject records. In addition, all source data should be attributable (signed and dated). The Investigator must therefore agree to allow direct access to all source data. Subjects must also allow access to their medical records, and subjects will be informed of this and will confirm their agreement when giving informed consent. If an Investigator or institution refuses to allow access to subject records because of confidentiality, arrangements must be made to allow an "interview" style of data verification.

A CRA designated by BioMarin will compare the CRFs with the original source documents at the study site and evaluate them for completeness and accuracy before designating them as "Source Data Verified" (SDV). If an error is discovered at any time or a clarification is needed, the CRA, or designee, will create an electronic query on the associated field. Site personnel will then answer the query by either correcting the data or responding to the query. The CRA will then review the response and determine either to close the query or re–query the site if the response does not fully address the question. This process is repeated until all open queries have been answered and closed.

Before a subject's CRF casebook can be locked, data fields must be source data verified and all queries closed. Refer to the Study Monitoring Plan for details on which fields must be source data verified. The Investigator will then electronically sign the casebook, specifying that the information on the CRFs is accurate and complete. The Data Manager, or designee, will then set the status of the forms, visits, and the entire casebook to Locked. Upon

Proprietary and Confidential

BIOMARIN	270-201 – Amendment 6	Page 95
----------	-----------------------	---------

completion of the CSR, an electronic copy of each site's casebooks will be copied to a compact disk (CD) and sent to each site for retention with other study documents.

BOMARIN	270-201 – Amendment 6	Page 96
---------	-----------------------	---------

